## **Appendix 4: Biweekly Phone Survey (Weeks 1, 3, 5)**

### **Effects of Supplemental Immunonutrition on Healing of Chronic Non-Healing Lower Extremity Ulcers in Diabetic Patients: Phone Survey**

- 1) **Intro:** "Hello (*Patient's Name*), this is (*research staff member's name*) calling from the office of \_\_\_\_\_ . I am calling regarding the research study you previously agreed to be enrolled in. Is now an okay time to speak?"
  1. **If No:** "Okay, when would be an acceptable time to call you back?"
  2. **If Yes:** *proceed to number 2*
- 2) **VAS Pain score:** "On a scale of 0-10, with 0 being no pain, and 10 being the worst pain possible, how would you rate your foot ulcer pain currently?"

#### **If the subject is enrolled in the treatment arm (received oral immunonutrition supplementation), proceed with questions 3 and 4. If not, skip to question 5:**

- 3) **Verification of supplementation:** "Did you receive supplementation and instructions on how it should be taken?"
  1. **If No:** "May I ask why not?"
  2. **If Yes:** *proceed to number 3*
- 4) **Medication compliance:** "Have you been able to take the supplementation daily as instructed?"
  1. **If No:** "May I ask why not?"
  2. **If Yes:** *proceed to number 3*
- 5) **Experienced symptoms:**
  1. "Have you experienced any of the following symptoms during your participation in the study. Please answer yes or no to each"
    - Abdominal pain, heartburn, nausea, vomiting, diarrhea, headache, insomnia, rash, indigestion, palpitations, numbness, bitter taste, low blood pressure, burping, taste perversion, constipation, gastrointestinal disorder, itchy skin, easy bleeding or bruising, red itchy welts
    - "Have you experienced any other symptoms"
      - If yes:** "can you please explain?"
      - If no:** *proceed to number 5*
- 6) **Emergency Department / Urgent Care Visits:** "Since beginning this study, have you had any unscheduled office visits, or have you been to any emergency departments or urgent care centers related to your foot ulcer?"
  1. **If Yes:** "Can you please explain?"
  2. **If No:** *proceed to number 6*

"Thank you for your time (*Patient name*), I hope you have a good day."

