**Visit 1: 2 Week Follow-up (First visit after completing 14 days of oral immunonutrition):**

- Provider documents characteristics of wound via PUSH Tool 3.0, captures clinical photos, obtains interval history, performs interval physical exam, and verifies and documents concomitant medications in the patient's chart.
- Provider visualizes and evaluates any additional wounds that are present and records characteristics in the patient's chart.
- Patient completes questionnaire in clinic (VAS, experienced symptoms since enrollment, review of supplement compliance).

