#### L-Arginine, 4.5 grams/day:

There is no recommended daily amount established for arginine supplementation. The observed safe level for oral administration is 9 grams/day and levels used in research vary from 2 to 30 grams/day. The daily supplementation provided to patients per this protocol is 4.5 grams/day, well below the upper threshold.

Possible side effects associated with L-arginine supplementation include abdominal pain, nausea, diarrhea, dyspepsia, palpitations, headache, numbness, bitter taste, and hypotension.

Noted above are the known side effects of the individual supplements. However, this specific combination of supplements has not been studied together in humans and therefore, the risks are unknown.

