**Continuous Patient Monitoring:**

Patients enrolled in this study will be flagged in EPIC as a participant in a research study. If a patient presents to an Emergency Department and/or is admitted to a Prisma Health hospital, the study team will be notified via EPIC. The patient's chart will be reviewed to determine the cause of the admission and promptly reported to the study investigators.

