**Adverse Event (AE) and Serious Adverse Event (SAE) Reporting:**

Adverse events will be recorded at in-office visits, via study coordinator phone calls, and through manual chart review. All AEs will be reported to the wound care provider, if they are not already aware of the event. Serious adverse events will be immediately reported to all study investigators.

Patients who experience an adverse event (AE) assessed as  $\geq$  Grade 3 (and  $\geq$  Grade 2 for bone marrow and cardiovascular events) per NCI-CTCAE version 5.0^19 will discontinue use of the oral supplement, if in the treatment arm. These subjects will continue to be monitored until the AE resolves or stabilizes. AEs and SAEs will be promptly reported to the IRB and FDA, as required.

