### **Biweekly Office Visits**

- Document characteristics of wound via PUSH Tool 3.0, obtain pressure profile reading (visits 0 and week 6), capture clinical photos, obtain interval history, perform interval physical exam, verify and document concomitant medications, visualize and record characteristics of additional wounds present.
- Patient completes questionnaire (VAS, experienced symptoms since enrollment, review of supplement compliance (if applicable))

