### **Appendix 3: Biweekly Clinic Survey (Weeks 2, 4, 6)**

## **Effects of Supplemental Immunonutrition on Healing of Chronic Non-Healing Lower Extremity Ulcers in Diabetic Patients: Clinic Survey**

Name: \_\_\_\_\_ Date: \_\_\_\_\_

1. Which follow-up visit are you being seen for today?  
 2-week visit  
 4-week visit  
 6-week visit
2. Did you receive immunonutrition supplements (Omega-3 fatty acids, Vitamin C, L-Arginine)?  
 Yes (proceed to question 3) \_\_\_\_\_  
 No (proceed to question 4)
3. Have you experienced any difficulty taking the supplementation according to the instructions?  
 Yes, please explain: \_\_\_\_\_  
 No
4. Have you experienced any of the following symptoms since your surgery? Check all that apply:  

 Abdominal Pain	 Low Blood Pressure
 Heartburn	 Burping
 Nausea	 Taste Perversion
 Vomiting	 Constipation
 Diarrhea	 Gastrointestinal Disorder
 Headache	 Itchy Skin
 Insomnia	 Easy bleeding or bruising
 Rash	 Red, itchy welts
 Indigestion	 Other, please explain: _____
 Palpitations	_____
 Numbness	
 Bitter Taste	
5. Have you made any trips to Emergency Departments/Urgent Care Centers since your last visit related to your foot ulcer?  
 Yes, please explain: \_\_\_\_\_  
 No
6. Circle your current level of pain related to your foot ulcer on the scale below:

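### Hypotension is a listed L-arginine risk, but its only explicit prompt is patient self-report, and no systemic blood pressure measurement is specified at baseline or follow-up in either arm

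*Combined protocol and SAP*

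**What the plan says.** **Risk.** The L-arginine part of Section 7 ends its list of possible side effects with "palpitations, headache, numbness, bitter taste, and hypotension". The same section then says that the three supplements have not been studied together in humans and that the risks of the combination are unknown.

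**Prompt.** The phone survey for weeks 1, 3 and 5 (Appendix 4, question 5) asks both arms for a yes or no to each symptom in a list that includes "numbness, bitter taste, low blood pressure, burping, taste perversion". The clinic survey for weeks 2, 4 and 6 (Appendix 3, question 4) has a matching checkbox under the question "Have you experienced any of the following symptoms since your surgery".

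**Other capture.** Section 9 states: "Adverse events will be recorded at in-office visits, via study coordinator phone calls, and through manual chart review". At the week 2, 4 and 6 visits the provider "obtains interval history, performs interval physical exam". Section 9 also provides an alert: "If a patient presents to an Emergency Department and/or is admitted to a Prisma Health hospital, the study team will be notified via EPIC".

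**Use of the data.** Section 9 grades adverse events by CTCAE version 5.0 and ties discontinuation of the supplement to the grade, with a lower threshold that covers "Grade 2 for bone marrow and cardiovascular events". The Data Safety Committee reviews the data after every 5 enrolled patients and decides whether the study continues.

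**The concern.** Low blood pressure is a measured quantity placed in a list of symptoms. A patient who has had no reading can neither confirm nor exclude it, so a yes or no depends partly on whether someone happened to take a pressure and tell the patient the result.

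The control arm receives standard of care alone and no placebo is described, so patients know their assignment. Those told that a supplement may lower blood pressure may report it more readily than controls. A recorded value in both arms is less open to this.

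At stake is how well a small first study of this combination can describe one named risk, and what the committee has before it at each review. The primary wound-closure outcome is not affected.

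**Working it through.** No sample size, power or event figure is involved, and the plan states no figure to reproduce. The check is a reading of every scheduled contact and data list for a systemic blood pressure or vital-sign measurement.

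**Step 1: scheduled contacts** (Section 6.f and its visit lists; Appendix 1)

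| Contact | Arm | Survey item on low blood pressure | Provider assessment listed | Systemic blood pressure listed |
|---|---|---|---|---|
| Visit 0 | both | no | wound, plantar pressure, photos, medications; no physical exam | no |
| Calls, weeks 1, 3, 5 | both | yes | none | no |
| Visits, weeks 2, 4, 6 | both | yes | interval history and physical exam, content not itemised | no |
| Safety follow-up, 6–8 weeks after week 6 | treatment only | no | adverse events recorded, wound viewed; may be virtual | no |

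Contacts: 4 office visits + 3 calls + 1 safety follow-up = 8, and 0 of 8 list a systemic reading. Appendix 1 agrees with 6.f. Its entry for the office visits ("obtain interval history, perform interval physical exam, verify and document concomitant medications") names no vital signs, and the pressure profile listed there is plantar pressure.

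**Step 2: data lists.** The key data points in 6.i contain no blood pressure or vital signs. ABI is there, but it is a ratio and has no timing. Toe blood pressure appears only as an inclusion criterion (6.b). Neither gives a systemic value followed over time.

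**Step 3: Section 9.** The monitoring paragraph announces laboratory and ECG monitoring. The items beneath it cover lipids, glucose, chemistry with hepatic enzymes, and INR/PT. No ECG is scheduled after enrolment, so no objective cardiovascular measurement is scheduled in either arm from then on.

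**Step 4: how far each route reaches.** Of the 6 post-baseline contacts up to week 6, 3 (the calls) rely on self-report alone. The other 3 add an exam and in-office adverse event recording.

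- The exam might include blood pressure, but nothing requires a reading or its entry in the study data. Visit 0 lists no exam, so no baseline is secured.
- Adverse event recording and chart review pick up what someone has already recognised.
- Hospital alerts are limited to emergency presentations and Prisma Health admissions. The surveys ask only about emergency or urgent care visits related to the foot ulcer, so they do not prompt for a visit elsewhere for low blood pressure.
- The clinic survey asks about symptoms since a surgery that is not part of this study, so 3 of the 6 survey prompts have an ill-fitting reference period. The phone survey asks about the period of study participation.

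**Step 5: what the fix would yield.** 30 patients × 4 visits = up to 120 readings. Of these, 30 would be baseline values, leaving up to 30 × 3 = 90 changes from baseline. These counts describe the remedy and do not estimate missed cases. No missed-case rate can be derived from the documents.

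**The case against.** The best case for the plan is that it has several routes to a hypotension event. Providers examine patients at three visits, adverse events are recorded there, charts are monitored throughout, and hospital contacts trigger an alert. The key data points are introduced as what the data include, so absence from the list does not prove that blood pressure is not taken. The exam is not itemised for any body system, so the silence is not particular to blood pressure. The committee reviews all recorded adverse events, not only survey answers. The arginine dose is half the observed safe level that Section 7 states (4.5 / 9 = 0.5). A patient told of a low reading can answer the survey item.

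Much of this stands, and it rules out several stronger readings that a reader might infer:

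- That hypotension is captured only by asking patients. Section 9 and the visit procedures contradict this.
- That all six post-baseline contacts depend on self-report. Only the three calls do.
- That cases could not be graded. A grading scale is named. How it classes or grades hypotension, and whether it falls under the lower cardiovascular threshold, is not in the documents.
- That blood pressure is never measured. It may well be taken in routine care.

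The objection does not supply a baseline value, a recorded follow-up value, or a requirement to obtain either. The other routes act on recognised events, and a symptom-free fall need not be recognised. The dose argument concerns how likely the event is, not whether it would be seen, and Section 7 itself calls the risks of the combination unknown.

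**Conclusion.** The point holds as a gap in measurement. Hypotension is a named risk, its only explicit prompt is patient self-report, and 0 of 8 scheduled contacts specify a systemic blood pressure reading in either arm. Recognised cases may be caught by other routes, but a symptom-free fall can be missed. The hypotension data that the plan assures in both arms on a common schedule are open-label survey answers, and these would carry the main between-arm comparison.

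This is worth correcting because the remedy is nearly free, but it does not threaten the primary analysis. The conclusion assumes that the lists in 6.f, 6.i, Section 9 and Appendix 1 describe what is required. If clinic readings are already taken in both arms, the remaining work is to state that they will be recorded or abstracted.

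**What to change.** - In Section 6.f and Appendix 1, specify that blood pressure is recorded, or the routine clinic reading abstracted, at visit 0 and weeks 2, 4 and 6 in both arms.
- Add it to the key data points in Section 6.i.
- Give the Data Safety Committee the change from visit 0 by arm at each of its reviews.
- In Appendices 3 and 4, keep the existing item and add a symptom that patients can report, such as light-headedness or fainting. Keeping the item preserves the only explicit prompt.
- Replace the reference to surgery in the clinic survey with the period of study participation, as in the phone survey.

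The cost is a few more data fields at visits that already take place and small changes to two survey forms. No extra visit or laboratory test is needed. No change to any dose or discontinuation rule is proposed.

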## **Appendix 5: Patient Satisfaction/Completion Survey**

### **Effects of Supplemental Immunonutrition on Healing of Chronic Non-Healing Lower Extremity Ulcers in Diabetic Patients: Completion Survey**

\*This survey should only be completed at the 6-week follow-up visit if you received the immunonutrition supplementation as a part of the research study\*

Name: \_\_\_\_\_ Date: \_\_\_\_\_

1. How satisfied were you with the immunonutrition therapy?  
 Very Unsatisfied  
 Unsatisfied  
 Neutral  
 Satisfied  
 Very Satisfied
  
2. Would you choose to follow the same therapy plan again, if you were to develop another foot ulcer?  
 Yes  
 No
  
3. Would you recommend this therapy to friends/family?  
 Yes  
 No
  
4. Do you feel the therapy aided in the healing of your ulcer?  
 Yes  
 No
  
5. How would you rate the difficulty in taking the supplementation?  
 Very Difficult  
 Somewhat Difficult  
 Neutral  
 Easy  
 Very Easy
  
6. How often did you forget to take the supplementation?  
 Never  
 Sometimes  
 Often  
 Almost Always
  
7. Did you experience any negative side effects from the supplementation therapy?  
 Yes, please explain: \_\_\_\_\_  
 No
  
8. Is there anything else you would like us to know about your experience with this therapy?  
\_\_\_\_\_

## Appendix 6: Supplement Compliance Log

Effects of Supplemental Immunonutrition on Healing of Chronic Non-healing Lower Extremity Ulcers in Diabetic Patients Compliance Log							
Date Consented:							
Date Supplement Received: <small>(Record the date that you were provided your supplements from Hawthorne Pharmacy)</small>							
Supplement Instructions:  Lovaza capsules Take 2 gel capsules by mouth daily.  Arginine/Vitamin C Powder Mix one scoop of powder into 8 oz water, juice, or gatorade and drink once daily.							
Instructions for completing compliance log: Week 1, Day 1 should be recorded as the first day AFTER you receive your supplements from Hawthorne Pharmacy. Indicate with a check mark when you take each supplement (2 Lovaza capsules and 1 Arginine/Vitamin C scoop) daily. Days should be consecutive. Do not skip days between doses. You will take these supplements every day for 6 weeks. Please be accurate in your reporting - ex - if you only take 1 Lovaza capsule on day 3, only record one check mark for this supplement.							
Week 1							
Day 1 Date:	Day 2 Date:	Day 3 Date:	Day 4 Date:	Day 5 Date:	Day 6 Date:	Day 7 Date:	
Lovaza capsule (2 capsules/day): _____	Lovaza capsule (2 capsules/day): _____	Lovaza capsule (2 capsules/day): _____	Lovaza capsule (2 capsules/day): _____	Lovaza capsule (2 capsules/day): _____	Lovaza capsule (2 capsules/day): _____	Lovaza capsule (2 capsules/day): _____	
Arginine/Vitamin C Powder (1 scoop/day): _____	Arginine/Vitamin C Powder (1 scoop/day): _____	Arginine/Vitamin C Powder (1 scoop/day): _____	Arginine/Vitamin C Powder (1 scoop/day): _____	Arginine/Vitamin C Powder (1 scoop/day): _____	Arginine/Vitamin C Powder (1 scoop/day): _____	Arginine/Vitamin C Powder (1 scoop/day): _____	
Week 2							
Day 1 Date:	Day 2 Date:	Day 3 Date:	Day 4 Date:	Day 5 Date:	Day 6 Date:	Day 7 Date:	
Lovaza capsule (2 capsules/day): _____	Lovaza capsule (2 capsules/day): _____	Lovaza capsule (2 capsules/day): _____	Lovaza capsule (2 capsules/day): _____	Lovaza capsule (2 capsules/day): _____	Lovaza capsule (2 capsules/day): _____	Lovaza capsule (2 capsules/day): _____	
Arginine/Vitamin C Powder (1 scoop/day): _____	Arginine/Vitamin C Powder (1 scoop/day): _____	Arginine/Vitamin C Powder (1 scoop/day): _____	Arginine/Vitamin C Powder (1 scoop/day): _____	Arginine/Vitamin C Powder (1 scoop/day): _____	Arginine/Vitamin C Powder (1 scoop/day): _____	Arginine/Vitamin C Powder (1 scoop/day): _____	
Week 3							
Day 1 Date:	Day 2 Date:	Day 3 Date:	Day 4 Date:	Day 5 Date:	Day 6 Date:	Day 7 Date:	
Lovaza capsule (2 capsules/day): _____	Lovaza capsule (2 capsules/day): _____	Lovaza capsule (2 capsules/day): _____	Lovaza capsule (2 capsules/day): _____	Lovaza capsule (2 capsules/day): _____	Lovaza capsule (2 capsules/day): _____	Lovaza capsule (2 capsules/day): _____	
Arginine/Vitamin C Powder (1 scoop/day): _____	Arginine/Vitamin C Powder (1 scoop/day): _____	Arginine/Vitamin C Powder (1 scoop/day): _____	Arginine/Vitamin C Powder (1 scoop/day): _____	Arginine/Vitamin C Powder (1 scoop/day): _____	Arginine/Vitamin C Powder (1 scoop/day): _____	Arginine/Vitamin C Powder (1 scoop/day): _____

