## 1) Background/Justification for Study

Diabetes mellitus is one of the most prevalent chronic diseases in the world and its incidence is expected to increase over the next 20 years. In 2018, approximately 34.2 million Americans (~10%) were affected with the disease. By 2050, the number of Americans diagnosed with diabetes is expected to exceed 48 million. Diabetes mellitus represents a group of metabolic disorders characterized by hyperglycemia and changes in the metabolism of other macronutrients. There are three main types of diabetes mellitus: Type 1, Type 2, and Gestational. Type 1 diabetics are unable to make insulin and are considered insulin-dependent, Type 2 diabetics are insensitive to insulin, and gestational diabetics develop insulin insensitivity, transiently, during or shortly after pregnancy. The etiology of disease may vary between types, yet the resulting pathophysiology is the same: poor peripheral blood flow, decreased cellular response at the injury site, elevated glucose levels, and poor nutrient transport. In addition, due to these mechanisms, some patients develop progressive neurologic dysfunction, called peripheral neuropathy, which affects the most distal nerves first. The late effects of peripheral neuropathy can lead to an insensate foot that is prone to ulceration and subsequent infection.

A common complication of diabetes-induced peripheral neuropathy is the development of diabetic foot ulcers (DFUs). While estimates vary, studies suggest that the average annual incidence of DFUs among diabetic patients may be as high as 6%. DFUs can have a devastating effect on patients' lives, often leading to debilitating injuries, amputations, and even death. It is estimated that foot ulcers are one of the major sources for hospitalization among diabetic patients and precedes up to 84% of lower limb amputations in these patients. In addition to the drastic impact to affected patients, DFUs represent a significant economic burden to the health care system and payers. Estimates place the total cost for management of diabetic foot ulcers between \$9-\$13 billion in addition to treatment and management of diabetes mellitus alone.

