Conventional treatment of DFUs including shoe wear modification, self-monitoring, local wound care, brace and shoe offloading, and surgical intervention. More sophisticated treatments including bioengineered cellular technologies and hyperbaric oxygen therapy have been used with limited success. However, these modalities are time consuming, burdensome, costly, and often do not treat the root cause of the problem. Additionally, even with proper care, wounds can take a significantly longer time to heal in diabetic patients. This is due to the altered physiology which does not allow for the proper nutrients and factors to mobilize to the site of injury, leaving wounds at high risk for infection and possible amputation.

In contrast to traditional treatment modalities, nutrition therapy has recently been shown to aide in healing of chronic wounds by providing essential nutrients which were not previously present in necessary amounts. Nutrition therapy has proven useful in modulating inflammation and the immune response, optimizing glucose control, and attenuating the hypermetabolic response to injuries, ultimately improving healing and recovery. Multiple studies have produced strong evidence that nutrition therapy reduces the incidence of complications including poor healing, infections, and development of hypertrophic scars. Thus, supplemental immunonutrition may offer a viable, low cost, rapidly scalable, and widely available approach to enhance the body's ability to heal itself.

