  - a. If randomized to the control group (SOC only), patients will receive standard of care defined as sharps debridement, appropriate dressing, and offloading. If randomized to the treatment group (SOC + Immunonutrition), subjects will receive standard of care defined as sharps debridement, appropriate dressing, and offloading in addition to a 6-week supply of Omega-3 fatty acids (soft gel form, 2 pills per day, total of 1.68 grams) and L-Arginine/Vitamin C (powder form, to be mixed with 8 oz liquid, 1 scoop once daily, total of 4.5 grams L-arginine and 500 mg vitamin C). Subjects will also be provided a compliance log with detailed instructions for taking and tracking supplements.
5. Patients will be scheduled for biweekly wound checks with their provider (weeks 2, 4, 6). Wound characteristics will be documented at each follow up visit using the PUSH Tool 3.0, images of the wound will be obtained, and an interval history and physical exam will be documented. The provider will verify and document concomitant medications in the patient's chart. The provider will visualize and evaluate any additional wounds that are present (new or present at time of enrollment) and record characteristics in the patient's chart. Patients will complete a questionnaire detailing their pain level (VAS), symptoms experienced during the treatment phase, and any unscheduled visits to emergency departments/urgent care centers. This will be completed via a paper survey in clinic during their office visit (Appendix 4). On weeks where an office visit is not scheduled (weeks 1, 3, 5), a research coordinator will call the patient and collect survey responses (Appendix 3).
6. At the final office visit (week 6), plantar pressure profiles will be recorded via the Tekscan Pressure Mat, and clinical plantar weight-bearing images will be captured. Patients randomized to receive the oral immunonutrition supplementation will complete an additional survey detailing their satisfaction with the treatment plan and any additional thoughts they would like to share (Appendix 5) and return the completed compliance log

(Appendix 6). Patients in the treatment arm will have CMP and lipid panel labs drawn at this timepoint or within 3 months of study completion.

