### **k. Withdrawal of Subjects**

Subjects may withdraw from the study at any time. All data recorded to that point may be kept and used for data analysis.

The provider has the authority to remove any subject from the study at his/her discretion, at which time the provider will inform the subject of withdraw. Circumstances for withdraw include, but are not limited to:

- a. Failure to meet inclusion/exclusion criteria (labs, A1c, ECG parameters)
- b. Lack of compliance with supplementation
- b. Rapid progression of wound(s) which is expected to result in surgery during the 6-week study period
- c. Severe adverse effects which are possibly related to supplementation

All data recorded to the point of withdraw may be kept and used for data analysis.

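### The treatment-arm compliance log lets patients with diabetes mix the daily powder in juice or a sports drink with no sugar-free qualifier; a one-line change to the log would remove this

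*Combined protocol and SAP*

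**What the plan says.** Section 6f (Procedures Involved, step 4a) describes the L-arginine/vitamin C product as "powder form, to be mixed with 8 oz liquid, 1 scoop once daily" and does not say which liquid. The same step makes the log the patient's working instruction: "Subjects will also be provided a compliance log with detailed instructions for taking and tracking supplements".

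Appendix 6 then names the liquids: "Mix one scoop of powder into 8 oz water, juice, or gatorade and drink once daily". On duration it says: "You will take these supplements every day for 6 weeks". Only the treatment arm receives the powder and the log.

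Section 6b requires a diabetes diagnosis and a hemoglobin A1c below 10% for everyone enrolled. No visible section restricts the mixing liquid or gives dietary advice to go with it. The consent pages and the log pages for Weeks 4–6 are not in the text available for review, so such advice could exist there.

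**The concern.** Patients will follow the log, and it offers two drinks that may contain sugar as daily vehicles for the study product, on equal terms with water. In a trial where every patient has diabetes and an open wound, that is an odd choice to leave open. The background section lists among the common features of the disease "decreased cellular response at the injury site, elevated glucose levels, and poor nutrient transport", and says in favour of the general approach that "Nutrition therapy has proven useful in modulating inflammation and the immune response, optimizing glucose control". The dose does not need a sweet vehicle, since water is already on the list.

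What is at stake is small: some treated patients may take a daily sugared drink because the study's own instruction offers it. Nothing in the visible log or in the surveys (Appendices 3 to 5) asks which liquid was used, so the investigators could not establish afterwards who did so.

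**Working it through.** The plan states no figure on this point, so there is none to reproduce. The check is a comparison of sections followed by an exposure count.

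**Comparison of sections**
- Section 6f leaves the liquid open; Appendix 6 gives examples. The two agree, and the log is the more specific.
- Neither excludes sugared drinks. Neither requires them, and water is listed first. A sugar-free version of the sports drink would also satisfy the log as written.

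**Inputs from the documents**
- Powder doses: one per day for 6 weeks (section 6f and Appendix 6).
- Volume of liquid per dose: 8 oz (same places).
- Treatment-arm size: 15 (sections 2 and 6c).

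**Input not in the documents (assumption)**
- Sugar per 8 oz serving: 0 g for water; 10–30 g for a sugared drink.

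**Exposure**
- Doses per patient: 7 × 6 = 42.
- Planned doses in the arm: 42 × 15 = 630.
- Liquid per patient: 42 × 8 oz = 336 oz.

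**Gross sugar per patient**, with *f* the fraction of doses taken in a sugared drink and *s* grams per serving: 42 × *f* × *s*.
- Always water (*f* = 0): 0 g.
- Half the doses (*f* = 0.5): 21 × 10 = 210 g to 21 × 30 = 630 g.
- Every dose (*f* = 1): 42 × 10 = 420 g to 42 × 30 = 1,260 g, that is 10–30 g per day.

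**Net difference between arms.** This cannot be computed. It depends on *f*, which is unknown. It also depends on whether the mix replaces a drink the patient already took, and on what controls drink, which the protocol does not restrict. Zero is a possible value.

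**Cost side.** If a less palatable mix led to the loss of one or two treated patients, the arm would lose 1/15 = 6.7% or 2/15 = 13.3%. The documents give no evidence that this would happen.

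**The case against.** The strongest reply is that this is a preference about beverage wording. The harm rests on a sugar content that the documents do not give, and on choices that patients may not make. The upper figure needs the sweetest option at all 42 doses with nothing else in the diet changed. That is fair, and it is why no net effect is claimed.

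Safeguards also exist. Enrolment caps A1c. Section 9 has chart glucose reviewed with alerts to investigators, emergency visits and admissions flagged, the supplement stopped for adverse events of Grade 3 or above (Grade 2 for some classes), and committee review after every 5 patients. Visits at weeks 2, 4 and 6 include history and examination, with calls in between. These reduce the risk but leave the instruction as it is. The glucose review uses routine data, with no study schedule or threshold; A1c is required only for eligibility; and the closing chemistry panel comes at or after the end of dosing.

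The choice of drinks may be deliberate. The listed arginine effects include "palpitations, headache, numbness, bitter taste, and hypotension". Compliance and satisfaction are Aim 2 and the tertiary outcome, and section 6k gives "Lack of compliance with supplementation" as a ground for removal. This is a real consideration, but it argues for flavoured drinks, not for sugar.

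A reader might infer three stronger points that the documents do not support:
- **That the instruction contradicts the trial's rationale.** The glucose statements in section 1 are general background. The case made there for the three nutrients concerns protein metabolism, nitric oxide, immune regulation, antioxidant action and collagen. Glucose control is neither an aim nor an endpoint.
- **That the arms will differ in sugar intake and the comparison is biased.** Only one arm gets the instruction, but a difference in instruction does not establish a difference in intake.
- **That the model in section 6h should carry a glycaemic covariate for this reason.** A baseline covariate would not adjust for drinks taken after randomization.

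**Conclusion.** The point holds as a minor, inexpensive patient-safety improvement. The instruction covers all 42 doses for each of 15 patients with diabetes and has no sugar-free qualifier. The gross amount ranges from 0 g to 420–1,260 g per patient over 6 weeks. The non-zero range rests wholly on the assumed 10–30 g per serving and on the patient always choosing a sugared drink.

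It does not show harm to glucose or healing, a between-arm imbalance, or a conflict between section 6f and Appendix 6. It has no bearing on sample size, power or type I error. It would fall away if the consent form or the unseen log pages already tell patients to use a sugar-free liquid.

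**What to change.** In Appendix 6, change the mixing liquid to *8 oz water or a sugar-free beverage*. Section 6f, step 4a, is not wrong and need not change; using the same wording there is optional and would keep the two places aligned.

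The cost is one line of text in the log. Dose, number of patients, visits and analysis stay as they are. The downside is possibly lower palatability, and with it lower compliance or satisfaction. Keeping sugar-free flavoured drinks on the list leaves patients a way to mask the taste and should largely ease this.
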